## **6.5. Study Drug Compliance**

Overall compliance (%) for the application of ruxolitinib cream during the CT and LTS period will be calculated as follows:

$$\text{Overall compliance (\%)} = 100 \times (\text{total number of nonmissing applications}) / (\text{total number of intended applications}),$$

where the total number of nonmissing applications is the total number of applications that the participant actually applied during the study and the total number of intended applications is the number of days in treatment – the number of days with an approved interruption.

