4. STUDY DESIGN

4.1. Overall Design

This is a Phase 3, open-label, 1-year safety study of ruxolitinib cream in adolescents (ages ≥ 12 years to < 18 years) with AD whose disease is not adequately controlled with topical prescription therapies or when those therapies are not advisable (see study design schema in Figure 1). The study will be conducted at approximately 40 sites in North America and Europe.

Approximately 100 participants with a diagnosis of AD (as defined by the Hanifin and Rajka [1980] criteria) with a duration of disease of at least 2 years, a total IGA score of 2 or 3, and %BSA affected by AD of 3% to 20% (excluding the scalp) will be enrolled.

All participants will apply ruxolitinib cream at the FDA-approved strength (1.5%) BID using the same treatment paradigm as the INCB 18424-303 and -304 Phase 3 AD studies, namely starting with an 8-week CT period during which participants will treat all baseline AD lesions, regardless of whether or not the lesion(s) improve, followed by a 44-week LTS period during which participants will only treat active AD lesions.

Participants who complete the Week 8 assessments with no safety concerns and with %BSA affected by AD no greater than 20% will continue into the LTS period.

During the LTS period (ie, starting at the Week 8 visit), the treatment regimen will continue to be ruxolitinib 1.5% cream BID; however, participants will only treat active AD lesions. Participants will have the next study visit at Week 12, and then subsequent study visits will occur every 8 weeks until the end of the study (44 weeks total in the LTS period and 52 weeks total in the study). At those study visits, AD lesions will be evaluated by the investigator to confirm if the participant still requires continuation of therapy (total IGA score \geq 1) or can otherwise (re)enter the observation/no treatment cycle (total IGA score = 0). Refer to Section 6.1 for further details.

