The start and end dates of treatment applications will be captured by the participant. Once the lesions clear, participants should continue to apply study cream for an additional 3 days to the areas of the body where lesions were last present before discontinuing treatment. If during this 3-day window the participant attends a study visit and the total IGA score is 0 at that visit, as assessed by the investigator, treatment is to be stopped. The date of the study visit will be recorded as the treatment cycle end date. If a lesion recurs, then treatment should be resumed at the first sign of recurrence.

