6.4. Study Treatment Compliance

Compliance will be assessed for frequency of application of study cream by reviewing the participants' eDiaries. Participants will also be questioned regarding study cream application technique, missed applications, and use of any additional topical or systemic prescriptions of other products or over-the-counter products. Compliance with study cream will be evaluated by the participant's adherence to the BID application regimen (evaluation of actual number vs prescribed number of applications) and documented by the site staff and monitored by the sponsor/designee.

Qualified clinical staff will review the eDiary entries for compliance. Participants will be considered compliant with the treatment regimen if they apply at least 80% but no more than 120% of the prescribed number of applications during participation in the CT period of the study. Participants who are noncompliant during the CT period and LTS period (if on a treatment cycle) will be reinstructed by the investigator (or designee), and the sponsor should be consulted by the investigator for instruction on the proper handling of the participant.

Drug accountability will be assessed by documenting the quantities of drug used between study visits (tube counts and weighing). At the first clinic visit and subsequent study visits, the amount of study cream to be applied is to be determined by weighing a tube before and after the participant applies a thin film of study cream to the affected areas. Participants will be instructed to bring all study cream with them to the study visits in order for site personnel to assess study cream accountability.

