6.5. Dose Modifications

There are no application adjustments/modifications allowed (decrease or increase in study cream strength or frequency of application) except for drug interruption or permanent discontinuation if needed (eg, for management of an AE).

Temporary interruption could be due to an AE during the CT or LTS periods or due to clearance of the AD lesions during the LTS period, as described in Section 6.1.

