6.5.1. Criteria and Procedures for Interruptions of Study Cream

Safety concerns should be discussed with the medical monitor immediately upon occurrence or awareness to determine whether the participant should continue or discontinue study cream.

In some circumstances, it may be necessary to temporarily interrupt treatment as a result of AEs or laboratory abnormalities that may have an unclear relationship to study cream. In the event that an AE is present only at a specific site of study cream application, treatment may be

temporarily withheld only at that lesional site and continued elsewhere. This should be recorded as a dose interruption on the AE eCRF page. Except in cases of emergency, it is recommended that any findings of concern (eg, AE) be confirmed and that the investigator consult with the medical monitor before interrupting study cream applications. Additionally, the investigator must obtain approval from the medical monitor before restarting study cream. Participants who experience a recurrence of the initial AEs upon restarting the study cream may need to permanently discontinue treatment with the study cream.

Participants should be closely monitored for the development of signs and symptoms of infection during treatment with the study cream and up to the safety follow-up visit. Study cream should be interrupted if a participant develops a serious infection, an opportunistic infection, or sepsis. Study cream application should not be resumed until the infection is controlled.

Instructions for interruption of study cream—related laboratory abnormalities are outlined in Table 7.

Table 7: Guidelines for Interruption and Restarting of Study Cream Due to Laboratory Abnormalities

AE Related to Study Cream	Action Taken
Any Grade 3 laboratory abnormality	Laboratory abnormalities should be confirmed with repeat testing within 48 hours whenever possible and immediate delivery of the laboratory results requested.
	• Interrupt study cream, based on clinical judgment in consultation with the medical monitor (whenever possible), taking into account the relatedness of the AE to the study cream and the participant's underlying condition.
	• Interruption may occur after the initial test result or may be delayed until or unless the repeat test confirms the laboratory abnormality; however, if the repeat test does confirm the laboratory abnormality, the study cream must be interrupted unless the medical monitor approves continuation.

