### Tables

Table No.	Title	Population
Baseline and Demographics Characteristics		
1.1 Disposition		
1.1.1	Analysis Populations	FAS
1.1.2.1	Summary of Participant Disposition in the CT Period	FAS
1.1.2.2	Summary of Participant Disposition in the LTS Period	LTS-EV
1.1.3	Summary of Number of Participants Enrolled by Country and Site	FAS
1.1.4.1	Summary of Protocol Deviations for the CT Period	FAS
1.1.4.2	Summary of Protocol Deviations for the LTS Period	LTS-EV
1.2 Demography and Baseline Characteristics		
1.2	Summary of Demographics and Baseline Characteristics	FAS
1.3 Baseline Disease Characteristics		
1.3	Summary of Baseline Disease Characteristics	FAS
1.4 Prior Medication and Concomitant Medication		
1.4.1	Summary of Prior Medications	FAS
1.4.2	Summary of Prior Medications for Atopic Dermatitis	FAS
1.4.3.1	Summary of Concomitant Medications in the CT Period	FAS
1.4.3.2	Summary of Concomitant Medications in the LTS Period	LTS-EV
1.5+ Others		
1.5	Summary of General Medical History	FAS
Efficacy		
2.1 IGA		
2.1.1.1	Summary of Participants Achieving IGA-TS by Visit	FAS
2.1.1.2	Summary of Participants in Each Category of IGA Score by Visit	FAS
2.1.1.3	Summary of Participants Achieving an IGA score of 0 or 1 by Visit	FAS
2.1.1.4	Summary of Participants Achieving a Facial IGA score of 0 or 1 by Visit	FAS
2.2 EASI		
2.2.1	Summary of Participants Achieving EASI75 by Visit During the Treatment Period	FAS
2.2.2	Summary of EASI Score by Visit During the Treatment Period	FAS
2.3 Itch NRS Score		
2.3.1	Summary of Participants Achieving $\geq$ 4-Point Improvement in Itch NRS Score by Visit During the Treatment Period	FAS with baseline Itch NRS score $\geq$ 4
2.3.2	Summary of By-Visit Itch NRS Score	FAS
2.3.3	Summary of Participant Achieving $\geq$ 4-Point Improvement in Daily Itch NRS Score	FAS with baseline Itch NRS score $\geq$ 4
2.3.4	Summary of Daily Itch NRS Score	FAS

Table No.	Title	Population
2.4 BSA		
2.4.1	Summary and Analysis of Total %BSA Affected by AD	FAS
Safety		
3.1 Exposure		
3.1.1.1	Summary of Exposure in the CT Period	FAS
3.1.1.2	Summary of Exposure in the LTS Period	LTS-EV
3.1.1.3	Summary of Exposure from Baseline to Week 52	FAS
3.1.2	Summary of Study Drug Compliance in the CT Period	FAS
3.1.3	Summary of Study Drug Compliance in the LTS Period	LTS-EV
3.2 Adverse Events		
3.2.1.1.1	Overall Summary of Treatment-Emergent Adverse Events in the CT Period	FAS

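### The SAP compliance formula divides applications by days with no factor of 2 for twice-daily use, so continuous-treatment compliance comes out at twice its true value, and the long-term figure also hangs on an unsettled rule for clear days.

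*SAP*

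**What the plan says.** SAP 6.5 gives overall compliance as 100 times non-missing applications divided by intended applications, for the CT and LTS periods. It then defines the two terms. The numerator is "the total number of applications that the participant actually applied during the study". For the denominator, "the total number of intended applications is the number of days in treatment" minus the days with an approved interruption. No multiplier for applications per day appears there or elsewhere in the SAP, and neither *days in treatment* nor *approved interruption* is defined.

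The protocol measures the same thing differently. Protocol 6.4 describes compliance as adherence to the twice-daily regimen, by "evaluation of actual number vs prescribed number of applications". Twice-daily use applies in both periods: Protocol 6.1 sets it out, and for the LTS period Protocol 4.1 says that "the treatment regimen will continue to be ruxolitinib 1.5% cream BID", on active lesions only. SAP 11.1 declares no change to protocol-defined analyses.

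On untreated days, Protocol 6.5 says a temporary interruption may arise from an adverse event "or due to clearance of the AD lesions during the LTS period". Protocol 6.5.1 also allows cream to be withheld at one lesion site while treatment goes on elsewhere, and adds: "This should be recorded as a dose interruption on the AE eCRF page".

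SAP Appendix A plans one compliance table per period: Table 3.1.2 for CT and Table 3.1.3, "Summary of Study Drug Compliance in the LTS Period". Listing 2.5 covers exposure and compliance.

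**The concern.** The denominator carries the label of a number of applications but is defined as a number of days. With two applications prescribed per treatment day, the ratio cannot be the percentage that Protocol 6.4 describes. Because SAP 11.1 declares no departure from the protocol, this is a slip and not an announced redefinition.

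The direction of the error matters: poor adherence is made to look good. Protocol 6.4 regards 80% to 120% of prescribed applications as compliant in the CT period. The SAP does not apply that band, so no planned classification changes. But a reader who sets the reported CT figures against it would accept participants who used about half the prescribed applications and would question those who used all of them.

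In the LTS period there is a second problem. Participants stop after lesions clear and resume on recurrence, so a large share of days may carry no prescribed application. Whether those days leave the denominator decides the answer, and SAP 6.5 does not say.

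In a one-year safety study, compliance helps the reader judge whether the safety data reflect the prescribed use.

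**Working it through.** The documents state no compliance result, so there is no figure to reproduce. The check applies the SAP 6.5 formula literally and compares it with the Protocol 6.4 definition.

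**Inputs**
- Prescribed applications per treatment day: 2 (Protocol 6.1).
- CT length: 8 × 7 = 56 days; the ±3-day window at Week 8 gives 53 to 59.
- LTS length: 44 × 7 = 308 days.
- Share of LTS days that are clear: not given. Assumed 25%, 50% and 75%, that is 77, 154 and 231 days.

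**CT period, numerator limited to CT**

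SAP as written: 100 × applications / days. Protocol: 100 × applications / (2 × days).

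| Applications in 56 days | Protocol definition | SAP as written |
|---|---|---|
| 112 | 112/112 = 100% | 112/56 = 200% |
| 89.6 | 89.6/112 = 80% | 89.6/56 = 160% |
| 67.2 | 67.2/112 = 60% | 67.2/56 = 120% |
| 56 | 56/112 = 50% | 56/56 = 100% |
| 44.8 | 44.8/112 = 40% | 44.8/56 = 80% |

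The number of days cancels, so the ratio is 2 for any CT length and any number of whole days interrupted. Only true adherence of 40% to 60% would appear inside the 80% to 120% band; true adherence of 80% to 120% would appear as 160% to 240%.

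**LTS period, every prescribed application made**

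| Clear days | Treated days | Applications | SAP, clear days kept (÷308) | SAP, clear days subtracted (÷treated days) | Factor of 2, clear days kept (÷616) | Factor of 2, clear days subtracted |
|---|---|---|---|---|---|---|
| 0 | 308 | 616 | 200% | 200% | 100% | 100% |
| 77 | 231 | 462 | 150% | 200% | 75% | 100% |
| 154 | 154 | 308 | 100% | 200% | 50% | 100% |
| 231 | 77 | 154 | 50% | 200% | 25% | 100% |

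Only the last column returns 100% throughout. Adding the factor of 2 while keeping clear days would report full adherence as 75%, 50% or 25%.

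**Two further points on the wording**
- *Numerator.* It is worded as covering the whole study. Set literally against a CT-only denominator, a fully adherent participant with 154 treated LTS days would show (112 + 308)/56 = 750%.
- *Interruptions at one lesion site.* Suppose 14 of 56 CT days carry such an interruption (assumed), with full twice-daily use elsewhere. If those days are subtracted, the SAP formula gives 112/42 = 267%, and the formula with the factor of 2 gives 112/(2 × 42) = 133%. If they stay in, the corrected figure is 112/112 = 100%.

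**The case against.** The strongest reply is that the formula line itself is right and only the explanation beneath it slips. With no declared change from the protocol, a programmer might supply the factor of 2 unprompted, and the sample displays, which are a separate document, may already do so. A summary near 200% would also look odd, since Protocol 6.1.1 caps use at twice daily. This makes the error conditional on literal programming. It does not remove it: the SAP is the governing text, its definition is complete, and an individual 50% shown as 100% would not look odd.

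On the LTS period, the protocol points towards removing clear days. Section 6.4 speaks of LTS non-compliance only for participants in a treatment cycle, no application is prescribed while lesions are clear, and 6.5 counts clearance as a temporary interruption. That is a fair reading and supports the fix below. But the SAP subtracts only *approved* interruptions, Protocol 6.1 states no approval step when a participant stops after clearing, and the nearest SAP definition, duration of treatment in 6.4, runs in calendar days from Day 1 to the last application. The lower LTS percentages do rest on the less natural reading and on assumed clear-day shares.

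A factor of exactly 2 also presumes a period-limited numerator and no lesion-site interruption days subtracted. Departures on either count push the CT figure higher still. Separate tables by period imply the numerator restriction, but the text should state it.

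Finally, the table is descriptive. That limits the weight of the point, but does not justify leaving the formula as it stands.

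**Conclusion.** The concern holds. Followed as written, SAP 6.5 reports CT compliance at twice its true value, whatever the period length, given a numerator limited to the CT period and no subtraction of days interrupted at one lesion site only. The LTS error is not a fixed factor: at full adherence the figure is 200% if clear days are subtracted, and 150%, 100% or 50% if they are kept, under assumed clear-day shares of 25%, 50% and 75%.

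Tables 3.1.2 and 3.1.3, and any percentage shown in Listing 2.5, would be affected. Treatment-emergent adverse event analyses, endpoints and analysis populations are not, and exposure in grams is summarised separately. It should be fixed, without suggesting that the safety conclusions depend on it.

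**What to change.** Replace the definition in SAP 6.5 with one that applies to each period separately:

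*Intended applications = 2 × (days in treatment in the period − days with an approved interruption of all application − days in an observation/no treatment cycle), with each day subtracted once.*

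And state that:
- the numerator counts only applications made in the same period;
- days with an interruption at a lesion site only stay in the denominator, because treatment continues elsewhere;
- recorded dates are used, with no partial-day rule;
- the Week 8 visit day belongs to one named period.

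The factor of 2 and the clear-day rule should go in together.

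The data are already collected. Daily applications are in the eDiary, and for treatment cycles Protocol 6.1 says: "The start and end dates of treatment applications will be captured by the participant". The text change is a few lines and the CT programming is trivial. The LTS programming must merge the cycle dates and separate full interruptions from those at one site.

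The cost in precision is small. Working from dates without times can misstate intended applications by up to 1 at each cycle start and 1 at each end. With 154 treated days (assumed; 308 intended applications), that is at most 2/308 = 0.6% for 1 cycle, 8/308 = 2.6% for 4 cycles and 20/308 = 6.5% for 10 cycles.

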## **6.6. Prior and Concomitant Medication**

For participants in the FAS population during the CT period, prior and concomitant medications will be coded using the WHO Drug Dictionary and summarized as number and percentage of participants with prior and concomitant medications by WHO drug class and WHO drug term. Additionally, separate prior AD therapy will also be summarized for the FAS population.

For participants in the LTS period, only concomitant medications will be summarized.

## 7. EFFICACY

[Appendix A](#) provides a list of data displays. Sample data displays are included in a separate document.

### 7.1. General Considerations

All by-visit analyses will include the follow-up period if the data are available.

[figure not shown]
### 7.2. Efficacy Hypotheses

[figure not shown]
Not applicable.

[figure not shown]
### 7.3. Analysis of Exploratory Efficacy Parameters

All efficacy analyses are exploratory. Hence, no p-values will be provided, and multiple adjustments will not be made.

#### 7.3.1. Exploratory Efficacy Measures

## **8. PHARMACOKINETICS AND PHARMACODYNAMICS**

### **8.1. Pharmacokinetic Analyses**

Trough plasma concentrations of ruxolitinib at 2 visits during the CT period will be summarized using descriptive statistics by visit. Mean trough plasma concentrations of ruxolitinib will be calculated for each individual and then summarized using descriptive statistics.

Trough saliva concentrations of ruxolitinib at 3 visits during the CT period and at 6 visits during the LTS period will be summarized using descriptive statistics by visit. Mean trough saliva concentrations of ruxolitinib will be calculated for each individual by period and then summarized using descriptive statistics.

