Pregnancy testing	X*	X		X	X	Section 8.3.5.1 *WOCBP will have a serum pregnancy test at screening and a urine test at all other visits. A positive urine test must be confirmed with a serum test.
PK blood and saliva sampling (trough)			Blood and saliva	Blood and saliva	Saliva only	Section 8.4; collected prior to study cream application at the clinic; the time of prior study cream application is to be recorded in the eCRF. Blood samples must not be drawn from an area that has been treated with study cream (or participants must not apply study cream from the previous application of study cream on the immediate body area where blood is to be drawn).

^a All assessments for the Week 8/EOT1 visit must be performed before participants may enter the LTS period.

VV-CLIN-017192 CONFIDENTIAL

Table 4: Schedule of Activities: Long-Term Safety Period

	LTS			Safety Follow-Up	
Visit Day (Range)	Weeks 12, 20, 28, 36, and 44 (± 7 d)	Week 52/EOT2 or ET (± 7 d)	Unscheduled Visits	30-37 d After Week 52/EOT2 or ET Visit ^a	Notes
Administrative procedures	•				
Contact IRT	X	X	X	X	Section 8.1.3
Prior/concomitant medications and procedures	X	X	X	X	Section 6.6
Apply study cream at site	X				Section 6.1.1; only for participants with active AD lesions at time of visit.
Weigh/dispense study cream and distribute reminder	X				Section 6.1.1 and Section 8.1.4
Collect/weigh returned study cream and review study cream eDiary compliance	X	X			Section 6.1.1 and Section 6.4
Record start and end dates of treatment cycle(s)	X	X			Section 6.1; the start/end date will have been recorded by the participant. The end date should be 3 days after lesions clear; however, if this 3-day window is during a study visit and total IGA score = 0, stop treatment and record the date of the study visit as the treatment cycle end date.
Assess study cream application compliance	X	X			Section 6.4
Assess Itch NRS eDiary compliance	eDiary compliance should be assessed routinely				Section 8.2.4
Safety assessments	•				
AE assessments and targeted physical examination	X	X*	X	X	Section 8.3.1 and Section 8.3.2.2; body systems with symptoms should be physically examined. *Targeted physical examination not performed at the Week 52/EOT2 or ET visit.
Comprehensive physical examination		X			Section 8.3.2.1
Body height and weight	X*	X			Section 8.3.3; height should be measured with a stadiometer and recorded *Week 28 only.

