Vital signs	X	X	X	X	Section 8.3.3; vital signs should be taken before blood/saliva sampling and other procedures.

Table 4: Schedule of Activities: Long-Term Safety Period (Continued)

		LTS		Safety Follow-Up	
Visit Day (Range)	Weeks 12, 20, 28, 36, and 44 (± 7 d)	Week 52/EOT2 or ET (± 7 d)	Unscheduled Visits	30-37 d After Week 52/EOT2 or ET Visit ^a	Notes
Disease severity assessments					
%BSA affected by AD	X	X	X	X	Section 8.2.2
Total IGA and facial IGA	X	X	X	X	Section 8.2.3
EASI	X	X	X	X	Section 8.2.5
Itch NRS		leted each evening t tudy cream during t			Section 8.2.4
Laboratory assessments					
Serum chemistries	X	X	X	X	Section 8.3.5
Hematology	X	X	X	X	Section 8.3.5
Pregnancy testing	X	X	X	X	Section 8.3.5.1; WOCBP will have a urine test at all visits. A positive urine test must be confirmed by a serum test.
PK saliva sampling (trough)	X*/†	X†/‡			*Collected prior to study cream application at the clinic. †The time of prior study cream application is to be recorded in the eCRF. ‡Not to be collected at the ET visit.

^a Except for participants who have been in an observation/no treatment cycle with a total IGA score of 0 (clear) from Week 48 or earlier until Week 52; such participants should complete the Week 52/EOT2 visit and this will also count as the safety follow-up visit.

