3. OBJECTIVES AND ENDPOINTS

Table 5 presents the objectives and endpoints.

Table 5: Objectives and Endpoints

Objectives	Endpoints		
Primary			
To evaluate the long-term safety and tolerability of ruxolitinib cream in adolescents with AD.	Incidence of TEAEs, assessed by monitoring the type, frequency, and severity of AEs.		
Secondary			
To further evaluate the long-term safety and tolerability of ruxolitinib cream in adolescents with AD.	Changes in vital signs, height, weight, and laboratory data for hematology and serum chemistry.		
To characterize the PK of ruxolitinib cream in adolescents with AD.	Trough concentrations of ruxolitinib at each postbaseline visit.		
Exploratory			

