8.2.3. Investigator's Global Assessment

Investigator's Global Assessment is an overall eczema severity rating on a 0 to 4 scale that will be assessed for the whole body (total IGA) and for the face only (facial IGA) during site visits as outlined in the SoA (see Table 3 [CT period] and Table 4 [LTS period]). The area "Face" is defined as including the area on the forehead to the original hairline, on the cheek to the jawline vertically to the jawline and laterally from the corner of the mouth to the tragus. The area "Face" will not include the surface area of the lips, scalp, ears, or neck but will include the nose and eyelids. The severity strata for the IGA are shown in Table 8.

Table 8: Investigator's Global Assessment

Grade	Severity	Status
0	Clear	No erythema or induration/papulation, no oozing/crusting; there may be minor residual discoloration
1	Almost clear	There may be trace faint pink erythema, with almost no induration/papulation, and no oozing/crusting
2	Mild	There may be faint pink erythema, with mild induration/papulation and no oozing/crusting
3	Moderate	There may be pink-red erythema with moderate induration/papulation and there may be some oozing/crusting
4	Severe	There may be deep or bright red erythema with severe induration/papulation and with oozing/crusting

Source: FDA 2012.

Participants must have a total IGA score of 2 or 3 at the screening and baseline visits to enroll in the study; there is no limitation for total or facial IGA score at Week 8 (baseline for the LTS period) to enter the LTS period.

During the LTS period, including Week 8 (baseline for the LTS period), total IGA will be evaluated by the investigator to determine whether the participant requires continuation of treatment or should (re)enter an observation/no treatment cycle. If the total IGA score is ≥ 1, the participant will start or continue active treatment with ruxolitinib cream 1.5% BID. If the total IGA score is 0 (clear), the participant will (re)enter an observation/no treatment cycle.

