8.4. Pharmacokinetic Assessments

Pharmacokinetic blood and saliva samples will be collected from all participants at the visits and collection times shown in the SoA (see Table 3 [CT period] and Table 4 [LTS period]) and as noted in Table 10.

The exact date and time of the PK blood and saliva sampling and the date and time of the last application of study cream preceding the blood or saliva sample (if applicable) will be recorded in the eCRF.

Instructions for sample preparation and shipping will be provided in the Laboratory Manual. Participants will receive reminders in advance of the study visit providing instructions to hold the application of study cream on the day of the visit and to record the time of the prior application of study cream.

Blood samples for PK must be drawn from an area that has not been treated with study cream, or if that is not possible, the participant must not apply study cream from the previous application of study cream on the immediate body area where blood is to be drawn (ie, for site visits in the morning, this means the application on the evening before [second dose of that day]; for site visits in the afternoon this means the application on the morning of the same day [first dose of that day]).

If blood is drawn from an area that has been treated with study cream, the site personnel must document the missed application at the location of the blood draw in the eCRF. After the PK blood or saliva sample is collected, participants will apply ruxolitinib 1.5% cream.

All analyses will be conducted by Incyte Corporation (Wilmington, DE) or Incyte's designee.

Table 10: Pharmacokinetic Blood and Saliva Sample Timing

Study Visit	Timing of Sample
CT period	Samples will be collected at any time prior to study cream application during study visits, but must be at least 4 hours after the previous application of study cream and after assessment of vital signs during the visit:
	Blood and saliva samples
• Week 2	Blood and saliva samples
• Week 4	Saliva sample only
• Week 8/EOT1 or ET	
LTS period: Weeks 12, 20, 28, 36, 44, and 52/EOT2	Saliva samples will be collected at any time prior to study cream application during study visits, but must be at least 4 hours after the previous application of study cream and after assessment of vital signs during the visit. No blood samples will be collected during the LTS period.

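### LTS saliva samples are all reported as trough, without separating participants on cream from those in a no-treatment cycle

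*SAP*

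**What the plan says.** SAP 8.1 plans two summaries of saliva. One is by visit: "Trough saliva concentrations of ruxolitinib at 3 visits during the CT period and at 6 visits during the LTS period will be summarized". The other is per participant: "Mean trough saliva concentrations of ruxolitinib will be calculated for each individual by period and then summarized using descriptive statistics". Neither has a condition on treatment status or on time since the last application.

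The word trough comes from the Protocol. The endpoint of the secondary PK objective (Protocol Table 5, repeated in SAP Table 1) is "Trough concentrations of ruxolitinib at each postbaseline visit", and the LTS saliva row of Protocol Table 4 carries the same label.

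On who is sampled, Protocol 8.4 says: "Pharmacokinetic blood and saliva samples will be collected from all participants at the visits and collection times". Table 10 sets a minimum of 4 hours since the previous application and no maximum. It schedules no blood sampling in the LTS period.

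On who is using cream in the LTS period, Protocol 8.2.3 says that with a total IGA score of 1 or more "the participant will start or continue active treatment with ruxolitinib cream". Otherwise: "If the total IGA score is 0 (clear), the participant will (re)enter an observation/no treatment cycle". Table 4 limits application at the visit ("only for participants with active AD lesions at time of visit") but puts no such limit on saliva sampling.

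The PK-evaluable population (Protocol 10.2, SAP 5.3.2) requires one application at any time and one postbaseline PK sample.

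**The concern.** In ordinary use, a trough is the concentration at the end of a dosing interval during treatment. In the LTS period, cream is used only on active lesions, and participants who clear stop until a lesion recurs. Some scheduled LTS saliva samples will therefore come from participants who have used no cream for weeks. SAP 8.1 counts these as troughs, both in the visit summaries and in each participant's LTS mean.

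LTS saliva is the only scheduled PK sampling after Week 8 in a one-year safety study. A low LTS value could mean little systemic drug while on cream, or simply that many participants were off cream. The summaries in SAP 8.1 cannot separate the two. The endpoint is descriptive and no hypothesis is tested, so what is at stake is how the result is labelled and read.

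**Working it through.** **1. The plan's visit counts.** From Protocol Table 10, continuous treatment (CT) saliva is taken at Weeks 2, 4 and 8 (3 visits). LTS saliva is taken at Weeks 12, 20, 28, 36, 44 and 52 (6 visits). These match SAP 8.1. The LTS share is 6/9 = 67% of the saliva visits.

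**2. Whether an off-cream sample can enter the LTS summary.** Each rule was followed in turn:
- Protocol 8.4 samples all participants.
- A sample taken weeks after the last application meets the 4-hour minimum.
- Protocol 6.1.1 rules out application at visits from Week 8 to Week 52 when IGA is 0, and Figure 1 sets no limit on the number of cycles.
- The PK-evaluable definition has no on-treatment condition.

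Nothing removes the sample. In the extreme case, a participant who applies no cream after Week 8 is outside the LTS-EV population (SAP 5.3.3) but can contribute six LTS trough values.

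**3. Time since last application.**
- Clear at Week 8 with no cream before Week 12: (12 − 8) × 7 = 28 days. The windows are ±3 and ±7 days, giving 28 − 10 = 18 to 28 + 10 = 38 days.
- Cycle ends at a later LTS visit with no cream before the next: 8 × 7 = 56 days. The windows are ±7 days at each end, giving 56 − 14 = 42 to 56 + 14 = 70 days.
- No cream in the whole LTS period: about 28, 84, 140, 196, 252 and 308 days at the six visits.

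**4. Effect on one participant's LTS mean.** Assume that off-cream values are near zero and on-cream values are similar across visits. With k of 6 visits off cream, the mean is (6 − k)/6 of the on-cream mean:

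| k | 1 | 2 | 3 | 4 | 5 | 6 |
|---|---|---|---|---|---|---|
| Factor | 0.83 | 0.67 | 0.50 | 0.33 | 0.17 | 0 |

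**5. Effect on a visit summary.** Let p be the off-cream share at a visit. The documents do not give it, so the values here are assumptions.
- Mean, with off-cream values near zero: pooled mean = (1 − p) × on-cream mean. This is 0.90 at p = 10%, 0.70 at p = 30% and 0.40 at p = 60%.
- Median, assuming only that off-cream values lie below all on-cream values: the pooled median is the on-cream quantile q that solves p + (1 − p)q = 0.5, so q = (0.5 − p)/(1 − p). At p = 0.1, q = 0.4/0.9 = 0.444. At p = 0.3, q = 0.2/0.7 = 0.286. Above p = 0.5 the median is itself an off-cream value.

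**6. CT samples.** All baseline lesions are treated throughout the CT period, so CT plasma and saliva have no planned off-cream cycles. Only samples during an interruption or at a CT early termination (ET) visit could be off cream.

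**The case against.** The best defence is that the SAP delivers the endpoint as the Protocol words it. The regimen under study is as-needed use, so an all-participant LTS mean is a fair description of exposure. That is right, and the summary should stay. What it does not support is the trough label, or the absence of any on-cream counterpart.

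A second reading is that only participants on cream are sampled. Table 4 says that LTS saliva is taken before application at the clinic, and Protocol 8.4 says that participants apply cream after sampling. That last sentence does not fit a participant with IGA 0, so the text is not perfectly clean. But the Table 4 note fixes timing. Week 52 saliva is scheduled although no cream is applied at that visit, Protocol 8.4 says all participants, and it asks for the last application time only where applicable.

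Third, Protocol 10.4.3 names percent BSA treated as a possible PK subgroup, which overlaps with cycle status because a participant in a no-treatment cycle treats none. However, it is optional, cycle status is not named, and SAP 8.1 plans no subgroup. Appendix A lists no PK displays, so the point rests on the text of SAP 8.1.

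Two objections stand as limits. The amount of dilution cannot be derived from the documents. The LTS-EV comparison is also not a contradiction, because that population is defined for safety analyses.

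**Conclusion.** The concern holds. Followed as written, SAP 8.1 reports off-cream saliva samples as troughs at any of the six LTS visits and in every affected participant's LTS mean. The visit counts and day ranges come directly from the schedule, given the scenarios in the working. The mean factors rest on near-zero off-cream values, with similar on-cream values across visits for the per-participant factors. The median shifts rest only on off-cream values being lower. The off-cream share p and the number of off-cream visits k are assumptions throughout, so the actual distortion is unknown.

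This should be fixed: it concerns a secondary endpoint and the remedy is cheap. It affects labelling and interpretation, not a test.

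**What to change.** Amend SAP 8.1, using the treatment-cycle dates and last-application times already collected (Protocol Table 4, 6.1 and 8.4).

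- **Split the LTS summaries.** Present LTS saliva by visit, and the per-participant LTS means, separately for on-cream and off-cream samples, with n in each. On-cream means that the sample falls within a recorded cycle (end date included), outside any recorded interruption, and after at least one application in that cycle. A cycle that starts at the visit counts as off-cream, because sampling precedes application. Visit IGA alone does not identify status.
- **Flag CT exceptions.** Apply the same flag to CT samples taken during an interruption or at a CT ET visit.
- **Keep the all-participant LTS summary**, described as exposure under as-needed use, and do not call off-cream values trough. State in SAP 11.1 how trough is defined for the Protocol endpoint, so that the two documents agree.
- **Carry the flag forward.** If LTS saliva is used in the concentration-hematology displays, show on/off status there too. Protocol 10.4.5 does not name the matrix.
- **Optional.** Report time since last application beside the on-treatment plasma and saliva summaries. It would show any long gaps within a cycle. No bias is claimed from samples taken 4 hours or more after application.

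The cost is SAP wording and programming, with no new data. The groups at each LTS visit will be smaller. On-cream samples will come mainly from participants with active or just-cleared disease, so the contributors change between visits; reporting n and keeping the all-participant summary make that visible. Cycle dates are participant-recorded, so some samples may be unclassifiable and should be counted as such.
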